7.9.1.5 Analysis Methods

The surgical success rate will be calculated as the proportion of subjects with a successful surgery, with a one-sided 97.5% confidence lower bound. This proportion will be tested against 85% using a Clopper-Pearson binomial exact test. The confidence lower bound needs to be greater than 85%, the p-value must be less than 0.025, to reject the null hypothesis.

7.9.1.6 Determination of Subjects/Data for Analysis

The analysis of the primary effectiveness will be based on the FAS but following the mITT principle for the conversion endpoint by excluding any subject with that endpoint missing.

7.9.1.7 Supporting Analyses

7.9.1.7.1 Poolability Analysis

An assessment of data poolability of the sites will be performed using the logistic regression with the outcome being surgery success (1=successful surgery, 0=converted surgery). A p-value of 0.15 or less will be considered significant (per FDA recommendation). Sites with fewer than five subjects will be combined into larger sites to ensure statistical robustness. If the sites are found to be significantly heterogeneous with respect to the primary endpoint, additional analyses will be conducted to further assess variations across sites in baseline and procedural variables that might contribute to the variations.

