14.10 Data Poolability

An assessment of data poolability of the sites will be performed using logistic regression for the primary effectiveness endpoint. A significance level of 0.15 will be considered (per FDA recommendation). Sites with fewer than five subjects will be combined into large sites to ensure statistical robustness. If the sites are found to be significantly heterogeneous with respect to the primary endpoint, additional analyses will be conducted to further assess variations across sites in baseline and procedural variables that might contribute to the variations.

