Cystectomy: The mean effect size is 0.141 with a 95% confidence interval of 0.095 to 0.205. The 95% prediction interval is 0.047 to 0.354. The 99% prediction interval is 0.024 to 0.520. A performance goal of

0.45 (45%), is clinically appropriate. A performance goal of 0.45, assuming a sample size of up to 31 (with 10% attrition n=27), one-sided alpha of 0.008 (Bonferroni Correction), and mean effect size of 0.141, results in a power of 83%.

With the consideration of both effectiveness and safety, a total of up to 141 subjects are planned to be treated in this study. Up to six study sites will be used. To keep enrollment balanced, each study site will be allowed to enroll no more than 30% of the total population.

7. Statistical Methods

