7.9.1.1 Hypothesis

The primary effectiveness hypothesis is to test if the surgical success rate is above the performance goal. Based on the Clinical Data Analysis of Robotic-Assisted Surgical Procedures in Urology Rev B (Medtronic on file), henceforth referred to as the Urology Clinical Data Analysis and clinical practice, a surgical success rate of 90% or higher is expected. To account for natural variability between sites, surgeons, and surgery types an overall performance goal of 85% (based on the literature) is pre-defined to evaluate the surgical success rate. Let P be the surgical success rate in this study. The statistical hypothesis is as follows:

$$H_0: P \leq 85\% \quad \text{vs.} \quad H_a: P > 85\%$$

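### The site-poolability test names no test statistic and has no rule for sites without conversions; at the plan's event rates that choice can decide the answer, and an exact test should be named

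*SAP*

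**What the plan says.** SAP 7.3 pools centers for every planned analysis on an assumption of homogeneity and defers the check of that assumption to SAP 7.9.1.7.1. There: "An assessment of data poolability of the sites will be performed using the logistic regression", with success coded 1 and conversion 0, and significance declared at 0.15. Protocol 14.10 matches it: "An assessment of data poolability of the sites will be performed using logistic regression for the primary effectiveness endpoint".

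The one provision for sparse data is "Sites with fewer than five subjects will be combined into larger sites to ensure statistical robustness". It counts patients, not conversions. The consequence of a significant result is "If the sites are found to be significantly heterogeneous with respect to the primary endpoint, additional analyses will be conducted"; no site-level follow-up of conversions is promised otherwise.

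Neither document says whether the p-value is Wald, likelihood-ratio or score, and neither mentions an exact or penalised method. On site numbers, SAP section 6 says "Up to six study sites will be used" and that "each study site will be allowed to enroll no more than 30% of the total population".

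**The concern.** Conversions are expected to be rare. When a site has none, the maximum-likelihood estimate of its log-odds is infinite. Software stops at a large finite value with a huge standard error, and the Wald statistic collapses towards zero. The likelihood-ratio and score statistics stay finite. The tests therefore part company most when all the conversions sit at one site, which is the case the check exists to find.

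At stake is the trigger for looking into site differences, and the evidence offered for the homogeneity assumption in SAP 7.3. Two programmers could follow the SAP faithfully and report opposite conclusions from the same data.

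**Working it through.** **Inputs from the documents.** Conversion rate 2.2% (protocol 14.4.1) or 2.4% (SAP 7.9.1.4) from the literature; 4.8% implied by the 95.2% success used for power (SAP section 6); at most 10% under the 90% expectation. N is 126 after attrition, up to 141 in all. Up to six sites, with a 30% cap (0.30 × 141 = 42).

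**Assumed, because the documents do not give them.** Site sizes: six near-equal (24, 24, 24, 23, 23, 23); six unequal within the cap (42, 35, 25, 18, 12, 9); four near-equal (36, 35, 35, 35).

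**1. The plan's own figure.** For n=126, the smallest rejecting count against 85% is 116 successes (at most 10 conversions). The exact one-sided level is 0.0131 and power at 95.2% is 0.959. The protocol states 0.96, so it reproduces. The documents give no operating figure for the poolability test.

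**2. Expected conversions.** 126 × 0.022 = 2.8, up to 141 × 0.048 = 6.8: about 3 to 7.

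**3. Chance that some site has no conversions.** P = 1 − ∏[1 − (1 − c)^nᵢ].
- Six near-equal sites, c=0.048: 0.952²⁴ = 0.307 and 0.952²³ = 0.323, so P = 1 − 0.693³ × 0.677³ = 0.897.
- The same sites, c=0.022: 0.978²⁴ = 0.586 and 0.978²³ = 0.600, so P = 1 − 0.414³ × 0.400³ = 0.995.
- Six unequal sites: 95% at 4.8%, 99.8% at 2.2%.
- Four near-equal sites: 54% at 4.8%, 89% at 2.4%.
- Six sites at 10% conversion (N=126–141): 41–73%.

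**4. One data set, two answers.** Seven conversions, all at one site of 24, N=141. Full log-likelihood: 7 ln(7/24) + 17 ln(17/24) = −14.49. Null: 7 ln(7/141) + 134 ln(134/141) = −27.84. The likelihood-ratio statistic is 2 × 13.36 = 26.7 on 5 df, p=0.00006. The joint Wald p from the same fit is 1.00. For a 6/1/0/0/0/0 split, Wald gives 0.66 and the likelihood ratio 0.001.

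**5. Rejection rates at 0.15** (40,000 simulated trials per row, N=141, near-equal sites; zero-conversion sites held at a logit of about −13 for Wald):

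| Sites | Conversion rates | Wald | Likelihood ratio | Exact | Firth LRT |
|---|---|---|---|---|---|
| 6 | all 2.4% | 0.0% | 8.5% | 9.8% | 0.3% |
| 6 | all 4.8% | 0.1% | 18.9% | 14.0% | 2.4% |
| 6 | one 20%, rest 1.8% | 6.1% | 85.2% | 81.1% | 57.1% |
| 6 | one 15%, rest 0.5% | 0.2% | 71.9% | 70.5% | 40.7% |
| 4 | all 2.4% | 0.0% | 17.1% | 7.6% | 1.9% |
| 4 | all 4.8% | 0.7% | 22.7% | 13.2% | 7.0% |
| 4 | one 20%, rest 1.8% | 33.2% | 94.9% | 91.0% | 88.8% |

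With one of six sites at 25% and the rest at 2.2%, Wald detects it in about 16–17% of trials, likelihood-ratio and score tests in about 92–98%, and the exact test in about 89–94%. These ranges put the poor site at one of the 24-patient sites or at the 42-patient site. At a very small site every test detects less.

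**The case against.** The strongest reply is that the Wald test is not in the plan. The documents say only logistic regression and a p-value. A likelihood-ratio or score test is a logistic-regression test, stays finite under separation, and has power equal to the exact test's. The score test also holds its level, at about 10–14% under homogeneity at 2.2–4.8% with six sites. This stands. A reader might infer that the stated method cannot honour the 0.15 level, or that the plan will declare sites poolable whatever happens. The documents support neither: both follow only if the Wald p-value is the one reported.

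Six sites is a maximum, and site sizes are assumed. With four sites or conversion near 10%, separation is much less certain. This also stands and limits the size of the problem.

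The analysis is supporting. A significant result changes neither the Clopper-Pearson test nor the performance goal. Correct.

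A reader might also infer that differences between surgery types go unexamined, since one 85% goal covers all three. SAP 7.9.1.7.3 already reports success by surgery type with a one-sided 97.5% lower bound, unconditionally, so no further test by type is asked for here.

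What none of this answers is that the choice of statistic is open and nothing covers sites without conversions.

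**Conclusion.** The point holds as an under-specified test with no provision for sparse events. With six sites at the plan's 2.2–4.8% conversion rates, separation is the normal case (about 89–99.8% of trials). The unstated choice then matters: under strong one-site heterogeneity, detection is about 16–17% by Wald and 92–98% by likelihood ratio or score. The likelihood-ratio test is not a clean default, because its null level runs from about 8% to 19% with six sites and up to 23% with four. The exact test stayed at or below 0.15 in the layouts examined, at a small cost in power; with equal sites at N=126 it is conservative (4.3% at 2.4% conversion, 8.7% at 4.8%).

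The harm is confined to a false assurance of homogeneity and the loss of the follow-up it would have triggered. The primary effectiveness result is not in question. The figures rest on the assumed site sizes and on the plan's own conversion rates proving about right.

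**What to change.** In SAP 7.9.1.7.1, replace the unspecified logistic test with a Fisher-Freeman-Halton exact test of the site-by-conversion table at 0.15. Add that subjects and conversions per site, with exact 95% intervals, will be tabulated whatever the p-value, so that site differences remain visible after a non-significant test. Align protocol 14.10, or record the change in SAP 7.12.

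A Firth-penalised likelihood-ratio test should not be offered as equivalent. It removes the separation, but with six sites its null rejection is 0.3–2.4% against a nominal 15%, and its power is 41–57% where the exact test has 71–81%.

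The cost is a sentence or two in the SAP, a standard procedure call and one small table. It needs no patients and no new data, and should be settled before the test is run.

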7.9.1.7.2 Sensitivity Analysis

If any primary effectiveness endpoint data are missing, up to two sensitivity analyses will be performed.

The first sensitivity analysis will use multiple imputation (MI) to impute missing outcome data if the percentage of missingness is greater than 5%. The model variables used for the MI analysis may include, but are not limited to: study site, age, gender, and indication for surgery. The fully conditional specification method with 10 burn-in iterations and 10 repetitions ($M=10$) will be used for imputation if MI is utilized.

Another sensitivity analysis will be a tipping point analysis with the missing outcome data. In this analysis, any missing primary outcome data will be imputed over a range of possible scenarios to determine the

proportion of subjects with missing data that would need to be converted to another form of surgery (e.g., open or laparoscopic) to change the primary effectiveness endpoint.

A listing of subjects with missing data, along with reasons for missing data, will be provided.

7.9.1.7.3 Sub-group Analysis by Surgery Type

The surgical success rate for each surgery type will be calculated as the proportion of subjects with a successful surgery, with a one-sided 97.5% confidence lower bound. Additionally, a summary of type of conversion (open, laparoscopic, or other RAS) will be provided.

7.9.2 Primary Safety Objectives

The primary safety objective of this study is to confirm that the Hugo™ RAS System is safe when used for urologic robotic assisted surgery. The primary safety endpoint is the rate of subjects with major complications (meeting Grade III criteria or higher per the Clavien-Dindo Classification system) from the first incision through 30 days post-procedure.

7.9.2.1 Hypothesis

The primary safety hypothesis is to test the major complication rate (Clavien-Dindo Grade III or higher) through 30-days post-procedure against a performance goal. Since the safety profiles (i.e., expected major complication rates) are very different among the three urologic procedures (nephrectomy, prostatectomy, cystectomy), a separate performance goal is pre-specified for each of the three procedures (as per FDA recommendation). The performance goals are determined based on published literature data as summarized in the Urology Clinical Data Analysis.

Let R be the 30-day major complication rate, and PG be performance goal for a specific surgery group. The statistical hypothesis is formulated as follows:

$$H_0: R \geq PG \quad vs. \quad H_a: R < PG$$

7.9.2.2 Endpoint Definition and Derivation

Rate of major complications within 30 days is calculated as the proportion of subjects who experience an AE with Grade III Clavien-Dindo classification or higher that is related to any of device, procedure, or underlying condition/disease prior to or during the 30 calendar-days post-procedure. The procedure date, AE start date, CEC-adjudicated relatedness (device, procedure, underlying condition/disease) and Clavien-Dindo Classification collected with the adverse event will be used to determine whether a related major complication was experienced within 30 days. The proportion of subjects experiencing a major complication must meet a performance goal based on the indication for surgery.

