Safety Assessments	
Adverse events (AEs) will be collected from the time of consent. Safety assessments will be based on the full analysis set (FAS). Data including AE event type, incidence, severity, duration, and procedure/device relatedness will be reported. AEs for all FAS subjects will be analyzed from first incision through the study exit.
 
AEs will be assessed by the Investigator and the sponsor as well as an external independent CEC for events requiring adjudication.
 
AEs occurring in subjects excluded from the full analysis set will be followed post-consent through study exit and will be reported in a listing in the clinical study report (CSR). These AEs will not be included in the FAS summary for either AE reporting or the analysis of the primary and secondary endpoints.

Statistics	Primary Analysis Set

Medtronic Business Restricted

This document is electronically controlled

CONFIDENTIAL 056-F275 Rev E Clinical Investigation Plan Template

The full analysis set (FAS) includes all enrolled subjects in whom the Hugo™ RAS procedure is begun, defined as the first skin incision. The FAS will be the primary analysis set for the evaluation of the primary and secondary endpoints.

Sample Size

A total of up to 141 subjects are planned to be treated in the study.

The sample size will provide more than 80% power to evaluate the primary effectiveness endpoint at one-sided alpha of 0.025. A performance goal of 85% is pre-defined to test the statistical hypothesis. Additionally, separate performance goals are pre-defined to assess the primary safety endpoint (rate of subjects with one or more major complications) for the three surgery types, and technical details are provided in **Section 14**.

Primary Hypothesis

The primary effectiveness hypothesis is to test if the surgical success rate is above the performance goal. The primary safety hypothesis is to test if the 30-day major complication rate is below the performance goal for each of the three surgery types. The major complication rate is defined as the rate of subjects with one or more adverse event meeting Grade \geq III per the Clavien-Dindo Classification system.

Other Information

All secondary endpoints and other prespecified outcome measures will be evaluated using descriptive statistics. Statistical analyses will be performed using SAS version 9.4 or higher.

4. Introduction

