5.1.3 Primary Endpoints

The primary effectiveness endpoint is the surgical success rate defined as the procedure not going into conversion. Conversion is defined as the switch from a robotic-assisted approach using the Hugo system to a robotic-assisted approach utilizing an FDA cleared robotic-assisted device, laparoscopic or open surgery.

The primary safety endpoint is the rate of subjects with complications meeting Grade III criteria or higher per the Clavien-Dindo Classification system¹ from the first incision through 30 days post-procedure.

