Major Complication Primary Endpoint: The rate of subjects with major complications (usually defined as Clavien-Dindo Grade \geq III) is a more commonly reported and clinically relevant measure than overall complications. The Expand URO study is designed to evaluate the three most complex and highest volume urology procedures.⁴ However, the procedural complexity, patient profile, and overall complication rates vary across the three procedure types. In the literature review, the overall complication rates varied from 0.2% (Hennessey 2018) to 53.3% (Abdul-Muhsin 2020) for radical nephrectomy and 0.5% (Covas Moschovas 2022) to 50% (Gaboardi 2019) for radical prostatectomy versus 1.4% (Tamhankar 2020) to 76% (Jeglinschi 2020) for radical cystectomy. Cystectomy procedures carry a particularly high risk of anticipated low-grade complications due to patient age and comorbidity. Therefore, the rate of overall complications may not be a clinically meaningful evaluation of device safety for radical cystectomy. Major complication rates range from 0.7% (Boga Long-term 2021) to 13.3% (Abdul- Muhsin 2020) for nephrectomy, 0.4% (Bahouth 2022) to 11.7% (Wilson 2020), versus 0.3% (Piazza 2022) to 19.7% (Arora 2020) for radical cystectomy in the literature review.

The primary endpoint for the Expand URO study is the 30-day rate of subjects with major complications (Clavien-Dindo Grade \geq III). The overall rate of subjects with any complications (Clavien-Dindo Grade \geq I) will be captured and reported as a secondary endpoint.

Other commonly reported safety measures (e.g., blood loss, transfusions, conversions, length of stay, reoperation, and readmission rates) will be also captured and reported to provide a comprehensive assessment of device safety.

- **Sample Size and Enrollment Proportions:** The sample size and performance goal estimates were derived from the literature search. The statistical design is therefore based on review of published data. A performance goal is specified for each of the three procedures. Additional details are provided in **Section 14**.
- **Follow-up Timeframe:** Based on the preponderance of data in the literature search, a 30-day primary endpoint was chosen for safety reporting. Oncologic subjects will be followed for 5 years.

Effectiveness:

Critical appraisal of the information collected in the literature review established the surgical success rate in order to assess the effectiveness of the Hugo™ RAS System.

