Complication	
Complications will be defined according to the Clavien-Dindo classification system.¹
 
Grade I: Any deviation from the normal postoperative course without the need for pharmacological treatment or surgical, endoscopic, and radiological interventions. Allowed therapeutic regimens are: drugs as antiemetics, antipyretics, analgetics, diuretics, electrolytes, and physiotherapy. This grade also includes wound infections opened at the bedside.
 
Grade II: Requiring pharmacological treatment with drugs other than such allowed for grade I complications. Blood transfusions and total parenteral nutrition are also included.
 
Grade III: Requiring surgical, endoscopic, or radiological intervention
 
Grade IIIa: Intervention not under general anesthesia
 
Grade IIIb: Intervention under general anesthesia
 
Grade IV: Life-threatening complication (including CNS complications)* requiring IC/ICU management
 
Grade IVa: Single organ dysfunction (including dialysis)
 
Grade IVb: Multiorgan dysfunction
 
Grade V: Death of a patient

Medtronic Business Restricted

This document is electronically controlled

CONFIDENTIAL 056-F275 Rev E Clinical Investigation Plan Template

	
NOTE 1: If the patient suffers from a complication at the time of discharge (see examples in Appendix 18.1), the suffix "d" (for "disability") is added to the respective grade of complication. This label indicates the need for a follow-up to fully evaluate the complication.
 
NOTE 2: *Brain hemorrhage, ischemic stroke, subarachnoidal bleeding, but excluding transient ischemic attacks. CNS, central nervous system; IC, intermediate care; ICU, intensive care unit.

Other	

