14.4.2 Primary Objective #2 (Safety)

The primary safety objective of this study is to confirm that the Medtronic Hugo™ RAS System is safe when used for urologic robotic assisted surgery. The primary safety endpoint is the rate of subjects with major complications (meeting Grade III criteria or higher per the Clavien-Dindo Classification system) from the first incision through 30 days post-procedure. Further details can be found in **Section 6.4.2**.

The primary safety hypothesis is to test the overall 30-day major complication rate (i.e., rate of subjects with one or more major complications) against a performance goal. Since the safety profiles or major complication rates are very different among the three surgeries, a separate performance goal is pre-specified for each of the three surgery types (as per FDA recommendation). The performance goals are determined based on published literature data.

Let R be the 30-day major complication rate, and PG be performance goal for a specific surgery group. The statistical hypothesis is formulated as follows:

$$H_0: R \geq PG \text{ vs. } H_a: R < PG$$

The hypothesis will be tested using the Clopper-Pearson exact method and the null hypothesis will be rejected if one-sided p-value is significant comparing to alpha determined after multiplicity adjustment as described in **Section 14.12**.

Performance Goal Rationale and Sample Size

The literature search was performed based on available literature for each of the three surgery types (nephrectomy, prostatectomy, cystectomy). Point estimates along with 95% and 99% predicted intervals were calculated to provide plausible range of potential effect sizes. Clinically meaningful margins and statistical precisions have been taken into account to determine the appropriate performance goals. In some situations, considerations were also given to align with the studies from comparable sample sizes. The calculation details and rationales are summarized in the following table.

All sample size calculations are based on exact test. Presuming a one-sample proportion and one-sided test with the least alpha of 0.008 (0.025/3) when performing three hypothesis testing (nephrectomy, prostatectomy, and cystectomy, respectively) and adjusting for multiplicity in primary safety objectives, sample size justification and performance goals are described as below:

Surgery Type	Performance Goal (PG)	Sample Size	Rationale

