4.1.2 Primary Safety Objective

The primary safety objective of this study is to confirm that the Medtronic Hugo™ RAS System is safe when used for urologic robotic assisted surgery. The primary safety endpoint is the rate of subjects with major complications from the first incision through 30 days post-procedure. A major complication is defined as Grade III or higher complication per the Clavien-Dindo Classification system.

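### SAP 7.9.2.2 counts only related Grade III+ events for the primary safety endpoint; the protocol and SAP 4.1.2 and 7.9.2 define that endpoint by grade alone

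*SAP*

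**What the plan says.** Four places in the two documents define the endpoint without reference to cause:

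- Protocol synopsis, Primary Hypothesis: "The major complication rate is defined as the rate of subjects with one or more adverse event meeting Grade" III or higher.
- Protocol 5.1.3: "The primary safety endpoint is the rate of subjects with complications meeting Grade III criteria or higher per the Clavien-Dindo Classification system". Protocol 14.4.2 tests the same quantity.
- SAP 4.1.2: "A major complication is defined as Grade III or higher complication per the Clavien-Dindo Classification system".
- SAP 7.9.2: "the rate of subjects with major complications (meeting Grade III criteria or higher per the Clavien-Dindo Classification system) from the first incision" through 30 days.

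Protocol Table 7 (section 12.4) does not bring cause in through the word complication either: "Complications will be defined according to the Clavien-Dindo classification system", followed by the grade definitions only.

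SAP 7.9.2.2, the derivation that will be programmed, counts a subject only if the Grade III+ event is one "that is related to any of device, procedure, or underlying condition/disease prior to or during the 30 calendar-days post-procedure". Relatedness is taken from CEC adjudication. The protocol has no matching text.

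**The concern.** Protocol 14.1 makes study success depend on this endpoint, and the two documents give it different numerators. A programmer who follows SAP 7.9.2.2 tests a different quantity from the one the protocol names, and the difference runs in one direction only, towards passing.

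Three further gaps make this harder to resolve from the plan as it stands:

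- SAP 7.9.2.2 does not say which ratings count as related. The rule that every rating except not related counts appears only in 7.9.2.7, for the exploratory analyses.
- No planned output shows what the filter removes. The 7.9.2.7 analyses are multiple imputation, the per-protocol set, and three subsets that narrow further by type of relatedness.
- No passage justifies the goals for a related-only rate. Protocol 6.4.2 describes the literature measure by grade: "The rate of subjects with major complications (usually defined as Clavien-Dindo Grade" III or higher.

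Secondary endpoint 1 (overall complication rate) has the same problem. SAP 7.9.3.1 filters it by relatedness, while protocol 5.1.4 and SAP 4.2 do not. That endpoint is descriptive and does not affect study success.

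**Working it through.** **Direction.** Protocol Table 7 includes a not-related class, so the filter can exclude events. Related Grade III+ events are a subset of all Grade III+ events in the same window. The denominator is the full analysis set either way (SAP 7.9.2.6). So the filtered count is at most the unfiltered count, and the one-sided p-value can only stay equal or fall. The same-window condition is needed because SAP 7.9.2.2 states no lower time limit, while SAP 7.9.2 and protocol 10.6 start at first incision.

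**Inputs.** Goals are 20% (nephrectomy, prostatectomy) and 45% (cystectomy). Sizes are n=49 and n=27 after 10% attrition, or at most 55 and 31. Planning rates are 2.9% and 14.1% (protocol 14.4.2). The test is one-sided exact binomial (SAP 7.9.2.5) with Holm over three tests at 0.025 (SAP 7.5), so the first step is 0.025/3 = 0.00833 and the last is 0.025.

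**Formulas.** The cut-off c is the largest count with P(X ≤ c | n, goal) ≤ alpha. Power is P(X ≤ c | n, planning rate).

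**The plan's own figures.** n=49: c=3, power 0.9466 (stated 95%). n=27: c=5, power 0.8287 (stated 83%). Both reproduce, and alpha 0.008 gives the same cut-offs as 0.00833.

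**What one subject changes.** Each cell shows the p-value at the cut-off, then with one more affected subject:

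| n, goal | First step (0.00833) | Last step (0.025) |
|---|---|---|
| 49, 20% | 3: 0.0067; 4: 0.0214 | 4: 0.0214; 5: 0.0547 |
| 55, 20% | 3: 0.0024; 4: 0.0087 | 5: 0.0245; 6: 0.0576 |
| 27, 45% | 5: 0.0038; 6: 0.0125 | 6: 0.0125; 7: 0.0338 |
| 31, 45% | 6: 0.0027; 7: 0.0085 | 8: 0.0226; 9: 0.0522 |

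If one subject's only Grade III+ event is adjudicated not related, a cohort one above its cut-off passes.

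**Illustration when the all-cause rate equals the goal.** Let u be the share of affected subjects whose Grade III+ events are all unrelated. No document gives u, so 0, 5% and 10% are assumed. The probability of passing is P(X ≤ c | n, goal × (1 − u)):

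| n, goal | First step, u = 0 / 5% / 10% | Last step, u = 0 / 5% / 10% |
|---|---|---|
| 49, 20% | 0.0067 / 0.0103 / 0.0158 | 0.0214 / 0.0314 / 0.0452 |
| 55, 20% | 0.0024 / 0.0040 / 0.0066 | 0.0245 / 0.0365 / 0.0532 |
| 27, 45% | 0.0038 / 0.0074 / 0.0136 | 0.0125 / 0.0222 / 0.0376 |
| 31, 45% | 0.0027 / 0.0055 / 0.0109 | 0.0226 / 0.0397 / 0.0663 |

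The last-step column applies to a cohort at its goal beside two that clearly pass. There 0.025 is exceeded at u = 5% for n=49, 55 and 31, and at u = 10% for all four.

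**Illustration at the planning rates.** If the planning rates are all-cause and u = 10%, the filter removes on average 49 × 0.029 × 0.10 = 0.14 subjects (0.16 at n=55), or 27 × 0.141 × 0.10 = 0.38 in cystectomy (0.44 at n=31). The probability of passing, P(X ≤ c | n, 0.9 × planning rate) against the unfiltered value, rises as follows:

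- First step: 0.9466 to 0.9612 (n=49), 0.9247 to 0.9446 (n=55), 0.8287 to 0.8813 (n=27), 0.8630 to 0.9105 (n=31).
- Last step: 0.9864 to 0.9911, 0.9949 to 0.9969, 0.9243 to 0.9528, 0.9763 to 0.9875.

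**The case against.** The strongest reply is that the filter may remove almost nothing. It keeps any event related to device, procedure or underlying condition. Underlying condition covers chronic disease present before surgery, events that cannot be assessed are rated possible, and the CEC is independent. Few Grade III+ events within 30 days of major urologic surgery would fall outside all of that. This stands, and it is why the size is left open. It also means that dropping the filter would cost the sponsor little.

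Second, the false-pass figures put the true all-cause rate at the goal, far above the planning rates, and the shares are assumed. They also judge a test of the related-only rate against the all-cause null; for its own quantity the test controls its error. This stands too. The excess over 0.025 measures the mismatch between the two definitions. It is not a flaw in the exact test or in Holm's method.

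Third, the literature analysis behind the goals is a sponsor file outside these documents, and whether the published rates were all-cause is not stated. So it cannot be said that the goals are miscalibrated, only that nothing in the plan ties them to a related-only rate.

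Fourth, unrelated events are not hidden. Thirty-day mortality is unfiltered, the sponsor reviews Grade IV events, and adverse events are tabulated and listed. That is so, but none of these is a Grade III+ subject rate.

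None of these points removes the contradiction between the derivation and the definition.

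**Conclusion.** The concern holds: SAP 7.9.2.2 is wrong as written against the protocol and against SAP 4.1.2 and 7.9.2. The text mismatch is certain. So is the direction, given the same window and denominator: the tested rate can only equal or fall below the rate the protocol defines.

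The size cannot be determined from the documents. It depends wholly on the share of affected subjects with only unrelated events, which may be zero. At an assumed 10% share and the planning rates, the chance of passing the first Holm step rises by about 0.015 to 0.02 in nephrectomy or prostatectomy and about 0.05 in cystectomy. No stated power or sample size is affected. This should be fixed before the analysis is run.

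**What to change.** **Default**, because the protocol and SAP 7.9.2 already read this way:

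- In SAP 7.9.2.2, define the numerator as subjects in the full analysis set with any adverse event of Clavien-Dindo Grade III to V starting from first incision through calendar day 30, whatever its relatedness. Naming the first incision also closes the missing lower time limit.
- In SAP 7.9.2.7, add the related-only rate as a supporting analysis and state which ratings count as related.
- Align secondary endpoint 1 in SAP 7.9.3.1 with its unfiltered definition in the same way.

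**Alternative**, if a related-only primary endpoint is intended: amend the protocol endpoint, justify the three goals for that rate, state which ratings count as related, and still report the all-cause Grade III+ rate.

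**Cost.** Two derivation lines and one supporting table. No new data are needed, since protocol 12.1 collects all adverse events through 30 (+7) days regardless of relationship. The observed rate may be slightly higher. As an unfavourable case, suppose the planning rates were in fact related-only (not stated) and 10% of all-cause subjects had only unrelated events, so that the all-cause rate is the planning rate divided by 0.9. Power would then change as follows:

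| n | First step | Last step |
|---|---|---|
| 49 | 0.9466 to 0.9272 | 0.9864 to 0.9796 |
| 55 | 0.9247 to 0.8989 | 0.9949 to 0.9916 |
| 27 | 0.8287 to 0.7599 | 0.9243 to 0.8821 |
| 31 | 0.8630 to 0.7975 | 0.9763 to 0.9564 |
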